Clinical Study Document

Study Title:

The Effect of Obesity on Contralateral Suppression in Patients with Multiple Sclerosis

NCT Number:

NCTXXX

Document Date:

August 14, 2025

Statistical Analysis Plan

Statistical Analysis Plan

Data were analyzed using SPSS version 21 (Statistical Package for the Social Sciences). The normality of the data was assessed using the Shapiro-Wilk test. Data were tested for conformity to a normal distribution. For normally distributed data, mean standard deviation ($\bar{x} \pm SD$) was used, while for non-normally distributed data, median (minmax) was reported. Students t-test was applied for comparisons between groups when data followed a normal distribution, whereas the Mann-Whitney U test was used for non-normally distributed data. Chi-square analysis was performed to evaluate relationships between categorical variables. Results were interpreted with a 95% confidence interval, and statistical significance was set at $P < 0.05$.

Sample Size Calculation

The sample size was calculated using G*Power (version 3.1.7). Based on a previous study that reported a large effect size (Cohens $d = 0.8$), an a priori power analysis was conducted. The analysis revealed that a total of 52 participants (26 per group) would be required to achieve a power of 0.80 with a significance level of 0.05 (two-tailed).

Study Protocol

Study Title

The Relationship Between Anthropometric Measurements and Efferent Auditory System in Patients with Multiple Sclerosis

Study Objectives

This study aims to investigate the relationship between anthropometric measurements (such as BMI) and the function of the efferent auditory system, measured by contralateral suppression of distortion product otoacoustic emissions (DPOAEs), in individuals diagnosed with Multiple Sclerosis (MS).

Study Design

This is a cross-sectional observational study. Participants will be assessed at a single time point within 12 months following their diagnosis of MS. Data collection will include demographic information, anthropometric measurements, and DPOAE testing with contralateral suppression.

Participants and Eligibility Criteria

Inclusion Criteria:

- Age between 18 and 50 years
- Confirmed diagnosis of Multiple Sclerosis
- Ability to cooperate with the procedures
- Normal ENT and otoscopic examination
- No history of noise exposure
- Not pregnant or menstruating (for female participants)

Exclusion Criteria:

- Presence of middle ear pathology
- Abnormal tympanometry
- Hearing loss > 20 dB HL between 500-4000 Hz
- Other neurological or psychiatric disorders
- Use of ototoxic medication
- History of otologic surgery or trauma

- BMI < 18.5 or > 40
- Diagnosis of metabolic or endocrine disorders

Study Procedures

Participants will complete a demographic questionnaire and undergo anthropometric measurement. DPOAE testing will be conducted in a sound-treated room using standardized protocols. Contralateral suppression will be measured by presenting noise to the opposite ear during DPOAE recording.

Ethical Considerations

The study has been approved by the Ondokuz Mays University Clinical Research Ethics Committee. All participants will provide written informed consent before participation. The study involves no risk to the participants and their personal data will be kept confidential.

Ethics Committee Approval (English Translation)

Institution

Ondokuz Mays University Clinical Research Ethics Committee

Details

Committee Registration Number: [Insert if available]

Address: [name]

[contact] ([name])

Email: [contact]

Approval Details

Date of Approval: June 11, 2025

Protocol Number: 2022/300

Applicant: [name]

Project Title: The Effect of Obesity on Contralateral Suppression in Patients with Multiple Sclerosis

Statement

The Clinical Research Ethics Committee of Ondokuz Mays University has reviewed and approved the above-mentioned research project in its session dated June 11, 2025, in accordance with the relevant ethical principles and national regulations on clinical research involving human participants.

This approval includes the review of the study protocol, informed consent forms, and participant information sheets. The researcher is responsible for conducting the study in compliance with ethical standards.

Signature

Signed on behalf of the Ethics Committee

[name]. [name]

Chair, Ondokuz Mays University Clinical Research Ethics Committee

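### The SAP names no unequal-variance test: harmless at the planned 26 per group, but Welch's t is a cheap safeguard if the groups end up unequal in both size and SD

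*Combined protocol and SAP*

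**What the plan says.** The Statistical Analysis Plan section sets out a rule with two branches. First, "The normality of the data was assessed using the Shapiro-Wilk test". Then "Students t-test was applied for comparisons between groups when data followed a normal distribution", "whereas the Mann-Whitney U test was used for non-normally distributed data". The descriptive summary switches with the branch, from mean and SD to median and range. The section adds "Results were interpreted with a 95% confidence interval", but names no difference estimate for the interval in either branch. It does not say whether normality is judged in each group or in all values together, and it mentions no Welch or other unequal-variance test.

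The Sample Size Calculation section concludes that "a total of 52 participants (26 per group) would be required", from Cohen's d = 0.8, power 0.80 and a two-sided 5% level. That is a calculation for a difference in means.

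Under Study Design: "This is a cross-sectional observational study". Neither the design nor the eligibility text describes a quota, matching or any other way of reaching 26 in each group.

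**The concern.** Student's t, in its usual meaning, pools the two variances. With equal group sizes that does little harm even if the SDs differ. With unequal sizes and unequal SDs together, the pooled standard error is wrong: too small if the smaller group is the more variable, too large if it is the less variable. A Shapiro-Wilk test looks at shape, not at spread between groups, so it offers no protection. In an observational study the group sizes depend on who is recruited, so the plan should not rely on exact balance.

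What is at stake is the error rate of the main two-group comparison, and whether the result is reported as a mean difference, the scale on which the study was sized.

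**Working it through.** **Inputs.** From the SAP: d = 0.8, 26 per group, two-sided 5%, power 0.80, and the Shapiro-Wilk, Student and Mann-Whitney rule. Assumed, because the documents give none: the splits 24/28, 22/30 and 16/36, the SD ratios, the skewness, and a 5% threshold for Shapiro-Wilk.

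**1. The plan's own figure.** For a two-sample t-test the noncentrality is d × √(n/2) = 0.8 × √13 = 2.88 with 50 degrees of freedom, which gives power 80.7%. Solving for 80% gives n = 25.5, so 26 per group and 52 in total. The stated N reproduces.

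**2. Why unequal size and SD matter.** The pooled t estimates the variance of the mean difference as s²p(1/n₁ + 1/n₂), where s²p = [(n₁−1)σ₁² + (n₂−1)σ₂²]/(n₁+n₂−2) in expectation. The true variance is σ₁²/n₁ + σ₂²/n₂. Take σ₁ = 1.5 and σ₂ = 1, with group 1 the smaller:

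- 26/26: pooled (25×2.25 + 25)/50 × 2/26 = 0.125; true 3.25/26 = 0.125. They are equal, so balance protects.
- 16/36: pooled (15×2.25 + 35)/50 × (1/16 + 1/36) = 1.375 × 0.0903 = 0.124; true 2.25/16 + 1/36 = 0.168. The pooled SE is √(0.124/0.168) = 0.86 of the true SE.

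The same formulas give the SE ratios in the table.

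**3. Simulated type I error.** Normal data, equal means, two-sided 5%. The rule was coded as Mann-Whitney if Shapiro-Wilk gives P<0.05 in either group, otherwise Student's t. Runs had 6,000 to 100,000 trials per setting; a range is shown where runs differ. The Monte Carlo SE is √(0.05×0.95/R): 0.28 points at R = 6,000, 0.15 at 20,000 and 0.07 at 100,000.

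| Split | SD ratio, smaller : larger group | Pooled SE / true SE | SAP rule | Welch |
|---|---|---|---|---|
| 26/26 | 1:1 | 1.00 | 5.1% | 5.0–5.1% |
| 26/26 | 2:1 | 1.00 | 5.3–5.7% | 4.9–5.2% |
| 24/28 | 1.5:1 | 0.97 | 5.7% | 4.9% |
| 22/30 | 1.5:1 | 0.94 | 6.5–6.9% | 5.0–5.3% |
| 16/36 | 1.5:1 | 0.86 | 8.8–9.5% | 5.1–5.4% |
| 22/30 | 0.67:1 | 1.06 | 3.9–4.0% | 4.9–5.1% |
| 16/36 | 0.67:1 | 1.16 | 2.6–2.7% | 4.8–5.2% |

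In the 1.5:1 rows Student's t alone gives 6.5% at 22/30 and 9.2% at 16/36, so the excess comes from pooling the variances and not from the normality check.

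**4. What the normality check does at 26/26.** If each group is tested at 5%, truly normal data go to Mann-Whitney in 1 − 0.95² = 9.8% of data sets; simulation agrees. If all 52 values are tested together, it is 5% with equal SDs and 21 to 22% with SDs 2:1. The effect on the verdict is small: relative to always using Student's t, the rule changes P<0.05 in 0.6 to 0.8% of data sets at d = 0.8 and in 0.3% under the null. Per-group and pooled testing lead to different verdicts in about 1% or less.

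**5. Swapping in Welch with the normality check kept.** In the 6,000-trial run, with the smaller group's SD 1.5 times larger, error falls from 6.8% to 5.4% at 22/30 and from 8.8% to 5.2% at 16/36.

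**6. Power at d = 0.8, normal data, equal SDs.** Welch v Student: 80.8% v 80.9% at 26/26, and 72.7% v 74.1% at 16/36.

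**The case against.** The strongest reply is that the plan states one design, 26 per group, and there nothing goes wrong: error is close to 5% and power is intact. The inflation needs unequal sizes and unequal SDs together, and the documents state neither. The 9% figure needs a 16/36 split, far from plan; at 24/28 it is only 5.7%. All of this stands, and it is why the point is minor.

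It may also be said that SPSS prints an unequal-variance row beside the pooled one. That is no answer, because the plan does not say which row will be used. Equally, pooled variance is the usual meaning of Student's t and not the SAP's own wording.

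A reader might infer more than the documents support:

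- *That the normality check itself inflates type I error or leaves the analysis open to choice.* The SAP writes down a rule, and with normal data at 26/26 its error is about 5.1 to 5.7%.
- *That the 5.3% of data sets at d = 0.8 in which Student and Mann-Whitney disagree on P<0.05 is the effect of the check.* It is not. It counts all data sets, including the roughly 90% in which Mann-Whitney is never selected. The check's own effect is the 0.6 to 0.8% above.
- *That a single Welch test is plainly better than the rule.* With skewed data and a pure shift at 26/26, Welch alone has 80.4% power against 82.6% for the rule (skewness 0.78), and 81.2% against 91.4% (skewness 1.75). The documents do not give the outcome's distribution, so this is a trade-off and not an error in the plan.

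**Conclusion.** The point holds as a minor, cheap improvement. At 26/26 with normal data the SAP's rule is sound. If the groups prove unequal in both size and SD, it is miscalibrated: about 6% (24/28), 6.5 to 6.9% (22/30) and 9% (16/36) if the smaller group's SD is 1.5 times larger, and about 2.7% at 16/36 if it is 0.67 times. Welch stays near 5% in all these settings. It is not perfect: with strong skew as well (skewness 1.75, 16/36, SD ratio 1.5) it gives 6.2%.

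The splits, SD ratios and distributions are assumptions. The documents neither state nor exclude unequal groups. Nothing here calls N=52 into question.

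**What to change.** **Change.** Replace Student's t with Welch's t wherever the SAP uses a t-test, and report the mean difference in suppression with its 95% CI. If Shapiro-Wilk is kept, say whether it is applied per group or to all values together.

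**Cost.** A wording change, plus a rerun if the comparison has already been made. N is unchanged. There is no power loss at 26/26, and about 1 to 1.5 points at 16/36 with equal SDs. This assumes one suppression value per participant and two defined groups; the documents do not define the groups, the ear or the DPOAE frequencies, and naming the mean difference does not settle those.

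**Optional, a matter of judgement.** Drop the normality check, make Welch the sole primary test, and always report Mann-Whitney with the Hodges-Lehmann shift and its 95% CI beside it. This fixes the quantity compared, but gives up about 2 to 10 power points if the data are skewed with a pure shift. If both tests are reported, name one as primary: counting either as positive has about 6% error at 26/26 with equal SDs and about 6.5 to 7% with SDs 2:1.

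**If the analysis is already done.** The SAP is in the past tense ("Data were analyzed using SPSS version 21"), which may suggest this. In that case label the change post hoc and also report the result under the SAP's existing rule, stating how normality was tested. Pre-specification cannot then be recovered, but the protection against unequal size and SD remains.

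### The comparison of non-randomised groups is wholly unadjusted; an age- and sex-adjusted estimate is a modest improvement once the BMI groups are defined, at a possible cost in power

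*Combined protocol and SAP*

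**What the plan says.** The Study Design section states "This is a cross-sectional observational study". The Statistical Analysis Plan section names a Shapiro-Wilk check and three inferential tests. For continuous outcomes, "Students t-test was applied for comparisons between groups when data followed a normal distribution", with Mann-Whitney U if the data are not normal. For categorical data, "Chi-square analysis was performed to evaluate relationships between categorical variables". No regression, covariate, matching or stratification appears anywhere in the document.

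The data for a simple adjustment are largely planned: "Data collection will include demographic information, anthropometric measurements, and DPOAE testing with contralateral suppression". Age has to be recorded to apply the criterion "Age between 18 and 50 years". Sex is implied by an inclusion criterion directed at female participants, but is not named as a questionnaire item.

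The target is worded in two ways. The cover title is "The Effect of Obesity on Contralateral Suppression in Patients with Multiple Sclerosis". The Study Objectives section is weaker: "This study aims to investigate the relationship between anthropometric measurements (such as BMI", and efferent auditory function. The Sample Size Calculation gives 26 per group without saying what the two groups are.

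**The concern.** Nothing allocates participants to BMI groups at random, so the groups may differ in age and sex. If either factor relates both to BMI and to suppression, the crude difference mixes its contribution with that of BMI and is biased as an estimate of an effect of obesity.

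The eligibility limits remove part of this. They exclude hearing loss above 20 dB HL, noise exposure, ototoxic drugs, and ear, other neurological, psychiatric, metabolic and endocrine disorders. Timing is also restricted: "Participants will be assessed at a single time point within 12 months following their diagnosis of MS". But no criterion balances age within the 32 years from 18 to 50, and none addresses sex. At stake is whether a significant result can be read in the way the cover title suggests.

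**Working it through.** **Inputs from the documents.** d = 0.8, two-sided alpha 0.05, power 0.80, 26 per group. Every relation of age or sex with BMI or suppression, the 70% female share and the BMI splits below are assumptions, because the documents give none of them.

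**1. The plan's own figure.** Two-sample t-test, noncentral t, df = 2n - 2 = 50, noncentrality d x sqrt(n/2) = 0.8 x sqrt(13) = 2.88. Power is 80.7% at 26 per group and 79.1% at 25. The stated 52 reproduces.

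**2. Bias of the unadjusted test when BMI has no effect.** Let age correlate r with BMI and r with suppression. Under a median split the groups differ by 2 x 0.798 = 1.596 SD in BMI, so by 1.596r SD in age, and the spurious difference in suppression is 1.596r² SD. This gives 0.064 SD at r = 0.2 and 0.144 SD at r = 0.3. Rejection rates at 26 per group (40,000 simulated trials per setting):

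| Assumed split | r = 0.1 | 0.2 | 0.3 | 0.4 | 0.5 |
|---|---|---|---|---|---|
| Median | 4.9% | 5.5% | 8.1% | 14.6% | 29.5% |
| Top 30% v other 70% | 5.2% | 5.5% | 8.3% | 15.7% | 32.2% |
| Top 30% v lowest 40% | 5.3% | 6.0% | 10.4% | 23.3% | 48.8% |

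For sex, with 70% female overall, the spurious difference is the gap in female share times the sex difference in suppression:
- 0.20 x 0.5 = 0.10 SD: 6.4% rejection
- 0.30 x 0.5 = 0.15 SD: 8.0%
- 0.40 x 0.8 = 0.32 SD: 19.2%

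A linear model with age and sex rejects 4.8% to 5.2% in all these settings, because the only confounder simulated is in the model.

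Mann-Whitney U behaves like the t-test. With a log-normal outcome, a median split and r = 0.3, 0.4 and 0.5 it rejects 7.4%, 13.9% and 27.4%. A rank-based model with age and sex rejects 5.0%, 5.1% and 5.4%.

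**3. Power of the adjusted analysis at an adjusted d of 0.8.** Formula: df = 48, noncentrality 0.8 x sqrt(13) x sqrt((1 - R²g)/(1 - R²y)). R²g is the share of group membership, and R²y the share of outcome variance, explained by age and sex. With age and sex independent, R²g = (0.798r)² + (gap/2)²/(0.7 x 0.3). For r = 0.3 and a 20-point gap this is 0.057 + 0.048 = 0.105.

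The two lost degrees of freedom alone take power only from 0.8075 to 0.8068. The formula ignores chance imbalance in the covariates, so the simulated column is the one to use; separate runs differ by about 0.01.

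| Setting | Formula | Simulated |
|---|---|---|
| Covariates balanced and irrelevant | 0.81 | 0.79 |
| Age only imbalanced, r with BMI = 0.3 / 0.4 / 0.5, not prognostic | 0.78 / 0.76 / 0.74 | 0.76 / 0.74 / 0.71 |
| Both imbalanced, neither prognostic (r 0.3, gap 20 points; 0.3, 30; 0.4, 30; 0.5, 40) | 0.76 / 0.73 / 0.71 / 0.63 | 0.75 / 0.72 / 0.70 / 0.64 |
| Covariates explain 10% / 20% of outcome variance, unrelated to group | 0.85 / 0.88 | 0.83 / 0.87 |

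**The case against.** The strongest reply is that the plan contains no error. The stated objective is a relationship, and for a crude association the unadjusted test keeps its level; the word effect appears only in the cover and project title. That stands, and it means association wording alone removes the mismatch in interpretation. It does not make the crude contrast the more informative one, since readers will ask whether a difference merely reflects age or sex.

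The second reply is that the harm is assumed. This also stands. At correlations of 0.1 to 0.2 the inflation is at most about one point. The largest figures need both correlations at 0.4 to 0.5, or a 40-point sex gap with a 0.8 SD sex effect, which the eligibility limits make unlikely.

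The third reply is that a covariate model cannot be fixed while the groups are undefined, and that adjustment can cost power. Both parts are right and are taken into the fix. In the settings where power falls most, age and sex are not prognostic, so they do not confound and adjustment gains nothing.

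A reader might infer that the planned comparison has a badly inflated false-positive rate, or that 52 participants is the wrong number. The documents support neither: they give no relation that would size the bias, and 52 is correct for the unadjusted test as specified.

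**Conclusion.** The point holds as a worthwhile improvement, not as a demonstrated error. The SAP describes no control of confounding in the analysis of a non-randomised comparison, and eligibility restriction covers only part of it. The size of the bias is unknown. Under equal age correlations and no BMI effect, the unadjusted test is within about one point of 5% at 0.2 or below and at about 8-11% at 0.3; higher values are possible but judged unlikely.

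It would be too strong to conclude that adjusting for age and sex makes the result an effect of obesity. The return to 5% in the simulations holds only because the adjusted factor is the sole confounder there. The documents describe no disease-severity or treatment data for adjustment. It would also be too strong to call the power loss an expected cost: power falls when age and sex predict group more strongly than outcome, and rises in the reverse case.

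**What to change.** 1. State which BMI groups are compared, with their limits. The model cannot be specified before this.
2. If the outcome data have not been analysed, make the primary between-group estimate a linear model of suppression on BMI group with age (continuous) and sex. Name one rank-based version with the same covariates for clearly non-normal residuals, and report the planned unadjusted test alongside.
3. If the data have already been analysed, keep the planned test and report the adjusted model as a post hoc supplementary analysis, labelled as such. The SAP is in the past tense and the protocol in the future tense, so the sponsor must say which case applies.
4. In either case, word the conclusion as an association.
5. State the power of the adjusted analysis at 26 per group: about 0.79 with irrelevant, balanced covariates, and from about 0.64 to 0.87 over the assumed settings.

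The change costs SAP wording, or one labelled extra analysis, using demographic data already planned; confirm that sex is among the recorded items. It takes two of 50 residual degrees of freedom and may lower power as shown. No increase in enrolment is proposed.

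### Must the SAP be changed because it names no primary test for obesity and contralateral suppression and judges every comparison at P < 0.05?

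*Combined protocol and SAP*

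**What the plan says.** The Statistical Analysis Plan is one paragraph. It checks normality with Shapiro-Wilk, compares groups by Student's t or Mann-Whitney according to the result, uses chi-square for categorical variables, and ends with a general threshold: "statistical significance was set at $P < 0.05". It names no primary outcome or contrast and has no multiplicity rule. It is written in the past tense ("Data were analyzed using SPSS version 21").

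The question is worded in two ways. The document title and the approved project title read "The Effect of Obesity on Contralateral Suppression in Patients with Multiple Sclerosis". The protocol's own Study Title and the Study Objectives speak of a relationship, in the latter case between "anthropometric measurements (such as BMI) and the function of the efferent auditory system". The Study Objectives name contralateral suppression of DPOAEs as the measure of that function.

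Sample Size Calculation describes one two-group comparison: "a total of 52 participants (26 per group) would be required to achieve a power of 0.80 with a significance level of 0.05 (two-tailed"). It does not say what the groups are or which outcome the effect size refers to. Every participant needs a "Confirmed diagnosis of Multiple Sclerosis", so the groups cannot be patients and healthy controls. The only BMI figures are the eligibility limits of 18.5 and 40. Study Procedures gives no frequency, ear or formula for suppression. Study Design says: "This is a cross-sectional observational study".

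**The concern.** Two of the three title statements point to an obese versus non-obese comparison of suppression, and the sample size fits that reading. The SAP never says so. The BMI cut-off, the choice of anthropometric measure, the ear and the frequency are all open, and each could produce another test of the main question at the same 0.05 threshold.

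If several such tests were run with equal standing, a reader could not tell the planned comparison from one picked out afterwards. The chance of at least one false positive would exceed 5%. Correcting for it by Bonferroni would take power below the stated 0.80 at 26 per group.

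**Working it through.** **1. The plan's own figure.** Inputs from Sample Size Calculation: d = 0.8, two-sided alpha 0.05, power 0.80, equal groups.

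- Normal approximation: n per group = 2(1.960 + 0.842)² / 0.8² = 2 × 7.85 / 0.64 = 24.5, rounded up to 25.
- Noncentral t: n = 25.52, rounded up to 26 per group, 52 in total. Exact power at 26 per group is 0.807.

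The stated 52 reproduces. A one-sided test would need about 21 per group, so the two-sided description also fits.

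**2. Error rate if k tests had equal standing.** The document does not give k, so 2 and 4 are assumptions. For independent tests the chance of at least one false positive is 1 − 0.95^k. For correlated tests it comes from a null simulation with 26 per group and equicorrelated normal outcomes (200,000 runs).

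| k (assumed) | Independent, by formula | Correlation 0.5 | Correlation 0.9 |
|---|---|---|---|
| 1 | 0.050 | – | – |
| 2 | 0.0975 | 0.090 | 0.070 |
| 4 | 0.185 | 0.157 | 0.095 |

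Measures from different ears or frequencies in the same person would be positively correlated, so the independence column is probably too high.

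**3. Power under Bonferroni.** The same t-test at alpha 0.05/k, d = 0.8:

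| k (assumed) | Power at 26 per group | n per group for power 0.80 |
|---|---|---|
| 1 | 0.807 | 26 |
| 2 | 0.716 | 31 |
| 4 | 0.617 | 37 |

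**4. What the text supports.** No row beyond k = 1 is documented. The t-test and Mann-Whitney are alternatives chosen by distribution, so they do not make two tests per outcome. Chi-square applies to categorical variables, whereas suppression is naturally a continuous measure. No list of ears, frequencies or outcomes appears. At 26 per group and d = 0.8, each t-test keeps alpha 0.05 and power 0.81 however many others are run. Only the familywise rate moves, and the document does not claim to control it.

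**5. Would naming one outcome bring a clear gain?** Suppose an effect of d = 0.8 is present in only half of two to four measures.

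- The average of all measures, with assumed correlation 0.5 to 0.9, has power 0.31 to 0.43. If the effect is in every measure, this rises to 0.83 to 0.95.
- One named frequency has power 0.81 if it is affected and rejects only 5% of the time if it is not.

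Neither choice is better in every case, and the document gives no information on which pattern to expect.

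**The case for a change.** The strongest case for a change is that the intended test can be inferred only in outline. A reader gets as far as two groups and suppression, but the cut-off, ear and frequency decide the P-value and cannot be deduced. The SAP sets a significance threshold and powers a test at two-sided 0.05, yet does not call itself exploratory. The two wordings of the question add to the ambiguity. Naming one outcome, contrast and test would keep 52 participants and power 0.81, at the price of a few sentences.

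The omission stands, and so does the mismatch between the titles. The consequence drawn from it is weaker:

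- The existence of several co-equal tests is supposed, not shown.
- The remedy would ask the sponsor to write down a cut-off, an ear rule and a frequency or average for which the document gives no basis. It would not replace a stated method with a better one.
- Making a BMI split primary would settle a question that the objective leaves open, since the objective describes a relationship.
- The cost may be more than wording. Nothing says that recruitment is by BMI group, so a fixed cut-off need not give 26 and 26. With 52 people split 35 to 17, power at d = 0.8 would be 0.756. Split 39 to 13, it would be 0.688.
- A label of exploratory would meet the multiplicity point just as well in a single-visit observational study with no stated confirmatory claim. If the data have already been analysed, as the past tense may suggest, it is the only honest option, because error control cannot be restored afterwards.

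**Conclusion.** No change to the plan is called for. This is a gap in specification, not a demonstrated error. The stated sample size is right for the one two-group test it describes (52 in total, power 0.81), and the general 0.05 threshold is an ordinary per-test convention. Inflation to about 7% to 10% with two tests, or 9% to 19% with four, depends on a number of tests and a correlation that the document does not give.

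The conclusion assumes that analysts fill the gap in the usual way: they report the groups and cut-off used, the ear and frequency or average analysed, and how many comparisons were made, and they do not present one selected result as the planned test. If a report claimed a confirmatory finding from one of many unlisted comparisons, the point would apply to that report.
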